2. STUDY DESIGN

N = Number of subjects planned to be enrolled; n = Number of subjects in each group; BS = Blood Sampling. Visit 3 and Visit 5 are applicable only for subjects in the Staggered group. Visit 4 is applicable only for subjects in the Co-administration group.

- Experimental design: Phase IV, open-label, randomised, controlled, multi-centric, single-country study with two parallel groups.
- Primary Completion Date: Visit 7 (Month 5)
- End of Study: Last testing results released of samples collected at Visit 7
- Study groups: The study groups and epoch foreseen in the study are provided in Table 1.

Table 1 **Study groups and epochs foreseen in the study**

| Study Groups | Number of subjects | Age (Min/ - Max) | Epoch |
|-------------------------|--------------------|--------------------|-----------|
| | | | Epoch 001 |
| Co-administration group | 146 | 6 weeks - 12 weeks | x |
| Staggered group | 146 | 6 weeks - 12 weeks | x |

- The study groups and treatment foreseen in the study are provided in Table 2.

Table 2 Study groups and treatment foreseen in the study

| Treatment name | Vaccine name | Study Groups | |
|----------------|--------------|-------------------------|-----------------|
| | | Co-administration group | Staggered group |
| Rotarix | HRV | x | x |
| Squarekids | Squarekids | x | x |

- Control: active control (Staggered group).
- Vaccination schedules: The vaccination schedules are as follows:
 - Subjects in the Co-administration group will be administered the DPT-IPV vaccine according to a 3, 4, 6 month schedule and the liquid HRV vaccine according to a 2, 3 month schedule.
 - Subjects in the Staggered group will be administered the DPT-IPV vaccine according to a 3, 4.5, 6 month schedule and the liquid HRV vaccine according to a 2, 3.5 month schedule.
- Treatment allocation: Randomised 1:1 using GSK Biologicals' central randomisation system on Internet (SBIR). The randomisation algorithm will use a minimisation procedure accounting for centre and stratified for a HRV immunogenicity sub-cohort.
- Blinding: Open-label.
- Sampling schedule: Details of the samples to be collected are as follows:
 - A blood sample of approximately 2 mL will be collected from a sub-cohort of subjects, 1 month after the administration of the second dose of the liquid HRV vaccine.
 - A blood sample of approximately 5 mL will be collected at Visit 7, 1 month after administration of the last dose of DPT-IPV vaccine from all the subjects.

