- Details of the HRV Immunogenicity sub-cohort are provided in Table 3. The sub-cohort will consist of 146 subjects (the first 73 subjects enrolled into the study from each study group).

Table 3 Sub-cohorts

| Sub-cohort name | Description | Estimated number of subjects |
|-------------------------------|--|--|
| HRV Immunogenicity sub-cohort | The serum anti-RV IgA antibody concentration and seropositivity 1 month after the second dose of the liquid HRV vaccine will be assessed in this sub-cohort of subjects. | 146 subjects (approximately half the number of subjects (73) from each study group)* |

* The first 73 subjects enrolled into each study group will be allocated to the sub-cohort.

- Recording of solicited local symptoms within 8 days follow-up period (Day 0 - Day 7) after the first dose of DPT-IPV vaccine.

- Recording of solicited general symptoms within 8 days follow-up period (Day 0 - Day 7) following administration of each dose of HRV vaccine and after the first dose of DPT-IPV vaccine.
- Recording of unsolicited symptoms within 31 days (Day 0- Day 30) following administration of each dose of HRV vaccine and after the first dose of DPT-IPV vaccine.
- Recording of causally related AEs from the first study vaccine up to Visit 7.
- Recording of SAEs from first study vaccine up to Visit 7.
- Recording of AEs/SAEs leading to withdrawal from the study from the first study vaccine.
- Recording of SAEs that are related to study participation (i.e. protocol-mandated procedures, invasive tests, a change from existing therapy) or are related to a concurrent GSK medication/vaccine from the time the subject consents to participate in the study until Visit 7.
- Type of study: self-contained.
- Data collection: Electronic Case Report Form (eCRF).

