4.2. Secondary endpoints

- Serum anti-RV IgA antibody concentration and seropositivity in a sub-cohort of subjects, 1 month after the second dose of the liquid HRV vaccine.
- Serum GMCs/GMTs for anti-diphtheria, anti-tetanus, anti-poliovirus serotypes 1, 2 and 3, anti-PT and anti-FHA antibodies, 1 month after the third dose of the DPT-IPV vaccine.
- Occurrence of solicited general symptoms during the 8-day (Days 0-7) follow-up period after each dose of liquid HRV vaccine.
- Occurrence of solicited local and general symptoms during the 8-day (Days 0-7) follow-up period after the first dose of DPT-IPV vaccine.
- Occurrence of unsolicited AEs during the 31-day (Days 0-30) follow-up period after each dose of the liquid HRV vaccine and the first dose of DPT-IPV vaccine, according to the Medical Dictionary for Regulatory Activities (MedDRA) classification.
- Occurrence of SAEs from the first dose of the study vaccine up to study end (Visit 7).

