5.1.1. Total vaccinated cohort

The TVC will include all subjects with at least one dose of the study vaccines administration documented:

- A safety and reactogenicity analysis based on the TVC will include all subjects with at least one vaccine administration documented.
- An immunogenicity analysis based on the TVC will include all subjects from this cohort for whom immunogenicity data were available.

The TVC analysis will be performed per treatment actually administered.

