6.4.2. Additional considerations

- In line with the endpoint description separate analysis will be made for solicited symptom, unsolicited AE within 31 days post vaccination and concomitant medication for
 - The 2 HRV doses
 - The first DTPa-IPV dose
- In line with the HRV project standard, the primary analysis of solicited symptom will be performed by administered dose regardless of whether a solicited symptom has been documented as present/absent. A complementary analysis by documented dose in which only dose for which presence/absence of the symptoms is recorded will be performed in case the percentage of documented dose among administered dose exceed 5% for one visit or a group.
- The incidence by dose, overall per dose and overall per subject of any grade 3 adverse event (solicited or unsolicited, local or general) with causal relationship to vaccination during the 8-day (Days 0-7) follow-up period will be tabulated with exact 95% CI.
- The percentage of subjects with unsolicited symptoms requiring medical attention occurring within 31 days (Days 0-30) post-vaccination with its exact 95% CI will be tabulated by group and preferred term. Similar tabulation will also be done for unsolicited AEs rated as grade 3 in intensity with causal relationship to vaccination.
- The percentage of subjects with causally related AEs from the first study vaccine until Visit 7 will be tabulated by group and preferred term.
- Medications will be coded using the GSKDRUG dictionary. Medications which started during the specified periods (Days 0-7 and Days 0-30) will be counted rather than all medications taken during the specified periods.
- For clinicaltrials.gov and EudraCT posting purposes, a summary of subjects with all combined solicited (regardless of their duration) and unsolicited adverse events will be provided. Solicited adverse events will be coded by MedDRA as per the following codes:

| Solicited symptom | Lower level code | Lower level term |
|----------------------------|------------------|---------------------------|
| Pain at injection site | 10022086 | Injection site pain |
| Redness at injection site | 10022098 | Injection site redness |
| Swelling at injection site | 10053425 | Injection site swelling |
| Fever | 10016558 | Fever |
| Irritability/Fussiness | 10057224 | Irritability postvaccinal |

| Solicited symptom | Lower level code | Lower level term |
|-------------------|------------------|------------------|
| Diarrhoea | 10012727 | Diarrhea |

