11.2.5. Safety

- For analysis of solicited, unsolicited adverse events (such as serious adverse events or adverse events by primary MedDRA term) and for the analysis of concomitant medications, all vaccinated subjects will be considered. Subjects who did not report the event or the concomitant medication will be considered as subjects without the event or the concomitant medication respectively.

- In case there will be more than 5% of subjects without documented dose for solicited symptoms (i.e., symptom screen not completed), sensitivity analysis will include only vaccinated subjects for doses with documented safety data (i.e., symptom screen completed).
- The following rules will be used for the analysis of solicited symptoms:
 - Subject who didn't document the presence or absence of a solicited symptom after one dose will be considered not having that symptom after that dose in the analysis done on "administered dose"
 - Subjects who documented the absence of a solicited symptom after one dose will be considered not having that symptom after that dose.
 - Subjects who documented the presence of a solicited symptom and fully or partially recorded daily measurement over the solicited period will be included in the summaries at that dose and classified according to their maximum observed daily recording over the solicited period.
 - Subjects who documented the presence of a solicited symptom after one dose without having recorded any daily measurement will be considered as having that symptom after that dose).
- The maximum intensity of local injection site redness/swelling will be coded as follows:

| Grade | Redness/swelling |
|-------|-------------------------|
| 0 | Absent |
| 1 | > 0 mm and \leq 5 mm |
| 2 | > 5 mm and \leq 20 mm |
| 3 | > 20 mm |

- For the analysis, temperatures will be coded as follows for oral, axillary or tympanic route:

| Grade | Temperature |
|-------|-------------------------------|
| 0 | < 37.5°C |
| 1 | \geq 37.5°C - \leq 38.0°C |
| 2 | > 38.0°C - \leq 39.0°C |
| 3 | > 39.0°C |

For rectal route, temperatures will be converted to axillary setting by subtracting 0.5°

- Note that for all tables described in this section, the way the percentage of subjects will be derived will depend on the event analysed (see table below for details). As a result, the N value will differ from one table to another.

| Event | N used for deriving % per subject for Vaccination phase | N used for deriving % per dose for Vaccination phase |

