|---------------------------|--|--|
| Concomitant vaccination | All subjects with study vaccine administered | All study visits with study vaccine administered |
| Solicited general symptom | Primary analysis: all subjects with study vaccine administered Sensitivity analysis: all subjects with at least one solicited general symptom documented as either present or absent (i.e., symptom screen completed) | Primary analysis: all study visits with study vaccine administered Sensitivity analysis: all study visits with study vaccine administered and with at least one solicited general symptom documented as either present or absent (i.e., symptom screen completed) |
| Solicited local symptom | Primary analysis: all subjects with study vaccine administered Sensitivity analysis: all subjects with at least one solicited local symptom documented as either present or absent (i.e., symptom screen completed) | Primary analysis: all study visits with study vaccine administered Sensitivity analysis: all study visits with study vaccine administered and with at least one solicited local symptom documented as either present or absent (i.e., symptom screen completed) |
| Unsolicited symptom | All subjects with study vaccine administered | All study visits with study vaccine administered |
| Concomitant medication | All subjects with study vaccine administered | All study visits with study vaccine administered |

- All CI computed will be two-sided 95% CI.

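### Read literally, the section 11.2.5 per-subject N for solicited local symptoms includes infants who never received DPT-IPV, which conflicts with the endpoint and with section 6.4.2

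*SAP*

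**What the plan says.** The denominator table in SAP section 11.2.5 (Annex 1) has this row: "Solicited local symptom | Primary analysis: all subjects with study vaccine administered". The general symptom row has the same N, and the rows for unsolicited symptoms and concomitant medication also use all subjects with any study vaccine. The opening rule of 11.2.5 agrees with the table: "all vaccinated subjects will be considered. Subjects who did not report the event or the concomitant medication will be considered as subjects without the event". Entry to the cohort is equally broad in section 5.1.1: "The TVC will include all subjects with at least one dose of the study vaccines administration documented".

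Local symptoms have a narrower collection rule. Section 2 plans "Recording of solicited local symptoms within 8 days follow-up period (Day 0 - Day 7) after the first dose of DPT-IPV vaccine", and the secondary endpoint in section 4.2 is "Occurrence of solicited local and general symptoms during the 8-day (Days 0-7) follow-up period after the first dose of DPT-IPV vaccine".

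The section 2 schedules are "the DPT-IPV vaccine according to a 3, 4, 6 month schedule and the liquid HRV vaccine according to a 2, 3 month schedule" for the Co-administration group and "the DPT-IPV vaccine according to a 3, 4.5, 6 month schedule and the liquid HRV vaccine according to a 2, 3.5 month schedule" for the Staggered group. In both groups the first vaccination is HRV alone, and DPT-IPV starts at the next visit.

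Section 6.4.2 adds: "In line with the endpoint description separate analysis will be made for solicited symptom", with the two HRV doses and the first DPT-IPV dose listed separately. It also says that the primary solicited-symptom analysis is by administered dose. It does not define N for either analysis.

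**The concern.** One HRV dose is enough to enter the Total Vaccinated Cohort and the 11.2.5 denominator. An infant who has that dose and then leaves before DPT-IPV dose 1 is never asked about injection-site pain, redness or swelling, and is not at risk of a reaction at a DPT-IPV injection site. Under the rule that non-reporters are event-free, the infant is nevertheless counted as a subject without a reaction.

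The secondary endpoint is local reactogenicity after DPT-IPV dose 1. A denominator that includes infants without that dose can only lower the reported percentage. The same wording would apply to the DPT-IPV dose 1 versions of the general symptom, unsolicited event and concomitant medication tables. A programmer following the Annex and one following the sense of 6.4.2 would obtain different values of N from the same data.

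**Working it through.** The SAP states no rate, precision or power figure that depends on this denominator, so there is no figure of the plan's own to reproduce. The check has two parts.

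**Which N does the text fix?**

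- Section 11.2.5 says that the way percentages are derived depends on the event, and refers the reader to its table. That table is the only place where N is set by event, and the local symptom row is not limited by vaccine.
- Section 6.4.2 calls for a by-administered-dose analysis of the first DPT-IPV dose. This implies recipients of that dose without saying so.
- Section 11.2.2 numbers study doses by vaccination visit, so study dose 1 is the HRV-only visit. An infant seen only at Visit 1 therefore has an administered dose.
- Template 20, the local symptom mock, defines N as subjects with an administered dose and names no vaccine. Template 19, which has a local symptom column, uses at least one administered dose. An HRV-only infant meets both definitions.

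**How large is the effect?**

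Let *n* be the number of vaccinated infants, *m* the number who never receive DPT-IPV dose 1, L = m/n, and *p* the local reaction rate among recipients of that dose.

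- Infants with a reaction: p × (n - m)
- Literal rate: p × (n - m)/n = p × (1 - L)
- Rate among recipients: p
- Understatement: p × L

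Neither L nor p is in the SAP. Assumed ranges are L from 1% to 5% and p of 20%, 40% and 60%.

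| L | p = 20% | p = 40% | p = 60% |
|---|---|---|---|
| 0% | 20.0% | 40.0% | 60.0% |
| 1% | 19.8% | 39.6% | 59.4% |
| 3% | 19.4% | 38.8% | 58.2% |
| 5% | 19.0% | 38.0% | 57.0% |

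In whole infants, with the planned 146 per group (Table 1) and p = 40%:

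| Lost before DPT-IPV dose 1 | Literal rate | Understatement |
|---|---|---|
| 1 | 0.40 × 145/146 = 39.7% | 0.3 points |
| 3 | 0.40 × 143/146 = 39.2% | 0.8 points |
| 7 | 0.40 × 139/146 = 38.1% | 1.9 points |
| 15 | 0.40 × 131/146 = 35.9% | 4.1 points |

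The last row is about 10% loss and is shown only as an outer case. For scale, the normal-approximation 95% half-width at 40% with 146 infants is 1.96 × √(0.40 × 0.60/146), or about 8 points.

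**Would the sensitivity analysis reveal it?** The documented-dose analysis in the same table would drop these infants, because they have no local symptom screen. Under 11.2.5 it runs only if more than 5% of subjects lack a documented dose, so a loss of 1% to 5% alone would not trigger it. Section 6.4.2 words the trigger the other way round, as documented doses exceeding 5% of administered doses. The two statements need reconciling.

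**The case against.** The strongest reply is that the SAP already points to the right population. Section 6.4.2 asks for a separate, by-administered-dose analysis of the first DPT-IPV dose, and an infant who never had that dose contributes none. The body of Template 20 is a single block, which suits a single-dose analysis. Annex 1 is a set of standard rules and itself says that N will differ between tables. Its rule for undocumented symptoms speaks of absence after a given dose, which presupposes that the dose was given. In the concomitant medication mock (Template 28), N falls from 508 to 499 and from 257 to 250 between doses 1 and 2, although its footnote also says at least one administered dose.

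Most of this stands as evidence of intent. A reader might therefore infer that the plan has settled on a diluted rate, and the documents do not support that. They contain a literal rule and an implied one that disagree. The reply does not remove the conflict, because no section states the implied N, 11.2.5 sends the reader to the table that states the wider one, and the mocks are illustrations copied from other studies.

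A reader might also infer that early loss could appear as a difference in local reactions between arms. The documents give no support for this. Both arms receive HRV alone at Visit 1, Table 4 gives them the same Visit 1 to Visit 2 interval (28 to 42 days), and section 7 rules out comparative analyses outside the confirmatory objectives.

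Finally, the SAP sections cited here do not state that HRV is given orally. The point does not need it: the endpoint concerns local symptoms after DPT-IPV dose 1, and an infant without that dose cannot contribute one.

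**Conclusion.** The point holds as an internal conflict in the SAP with a small numerical effect. The 11.2.5 row, taken as written, includes infants who never received DPT-IPV; the endpoint and section 6.4.2 imply that they should be left out.

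If the literal rule were programmed, the rate would be understated by p × L. For a true 40% that is 0.4 to 2.0 points at an assumed loss of 1% to 5%, and nothing if every vaccinated infant reaches DPT-IPV dose 1. At those losses the understatement is well inside the sampling uncertainty for 146 infants per group. It affects a descriptive secondary endpoint and none of the non-inferiority criteria. The size rests on assumed values of L and p; the direction does not.

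**What to change.** In the 11.2.5 table, set the primary per-subject N for solicited local symptoms to *all subjects who received the first dose of DPT-IPV vaccine*. In 6.4.2, state the same N for the DPT-IPV dose 1 analyses of solicited general symptoms, unsolicited adverse events and concomitant medication.

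Correct the per-dose N in the same row at the same time. It is all visits with any study vaccine: four in the Co-administration group and five in the Staggered group under the section 2 schedules. Local symptoms are solicited after only one of these. With full attendance, a 40% rate after DPT-IPV dose 1 would read 40/4 = 10.0% and 40/5 = 8.0% per dose. The matching N is visits at which the first DPT-IPV dose was given.

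The cost is a line or two of SAP text and a filter in the programs, with no new data. Reported local reaction rates would be the same or slightly higher than under the literal per-subject rule.

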11.2.6. Data presentation description

The following decimal description from the decision rules will be used for the demography, immunogenicity and safety/reactogenicity.

| Display Table | Parameters | Number of decimal digits |
|-----------------------------|--|--------------------------|
| All summaries | % of count, including LL & UL of CI | 1 |
| Demographic characteristics | Mean, median, SD | 1 |
| Immunogenicity | % of difference, including LL & UL of CI | 2 |
| Immunogenicity | Anti-RV IgA GMC | 1 |
| Immunogenicity | Anti-diphtheria and anti-tetanus GMC | 1 |
| Immunogenicity | Anti-poliovirus serotypes 1, 2 and 3 GMT | 1 |
| Immunogenicity | Anti-PT and anti-FHA GMC | 1 |

12. ANNEX 2: SUMMARY ON ELIMINATION CODES

Refer to Section 5.2.

|-------------|--|----|
| Template 29 | Incidence of solicited general symptoms reported during the 7-day (Days 0-6) post-vaccination period following each dose and overall (Total vaccinated cohort)..... | 49 |
| Template 30 | Number (%) of subjects with serious adverse events from first study vaccination up to Visit 7 including number of events reported (Total vaccinated cohort)..... | 50 |
| Template 31 | Solicited and unsolicited symptoms experienced by at least 5 % of subjects classified by MedDRA Primary System Organ Class and Preferred Term within 31-day (Days 0-30) post-vaccination period after any dose of liquid HRV vaccine and first dose of DPT-IPV vaccine - SAE excluded (Total vaccinated cohort)..... | 50 |
| Template 32 | Number of enrolled subjects by age category (Total vaccinated cohort)..... | 51 |

Template 1 Number of subjects by centre (Total vaccinated cohort)

| Center | HRV | Placebo | Total | |
|--------|-----|---------|-------|------|
| | n | n | n | % |
| PPD | 26 | 14 | 40 | 5.2 |
| PPD | 28 | 14 | 42 | 5.5 |
| PPD | 18 | 8 | 26 | 3.4 |
| PPD | 26 | 13 | 39 | 5.1 |
| PPD | 18 | 10 | 28 | 3.7 |
| PPD | 12 | 7 | 19 | 2.5 |
| PPD | 13 | 7 | 20 | 2.6 |
| PPD | 38 | 19 | 57 | 7.5 |
| PPD | 13 | 7 | 20 | 2.6 |
| PPD | 68 | 34 | 102 | 13.3 |
| PPD | 32 | 16 | 48 | 6.3 |
| PPD | 14 | 7 | 21 | 2.7 |
| PPD | 16 | 8 | 24 | 3.1 |
| PPD | 6 | 4 | 10 | 1.3 |
| PPD | 48 | 24 | 72 | 9.4 |
| PPD | 48 | 24 | 72 | 9.4 |
| PPD | 72 | 35 | 107 | 14.0 |
| PPD | 3 | 2 | 5 | 0.7 |
| PPD | 3 | 2 | 5 | 0.7 |
| PPD | 6 | 2 | 8 | 1.0 |
| All | 508 | 257 | 765 | 100 |

n = number of subjects included in each group or in total for a given centre or for all centres

All = sum of all subjects in each group or in total (sum of all groups)

% = n/All x 100

Centre = GSK Biologicals' assigned centre number

Template 2 Number of subjects vaccinated, completed and withdrawn with reason for withdrawal at Visit 4 – First year conclusion (Total vaccinated cohort)

| | HRV | Placebo | Total |
|---|-----|---------|-------|
| Number of subjects vaccinated | 508 | 257 | 765 |
| Number of subjects completed | 492 | 247 | 739 |
| Number of subjects withdrawn | 16 | 10 | 26 |
| Reasons for withdrawal : | | | |
| Serious Adverse Event | 1 | 0 | 1 |
| Non-serious adverse event | 0 | 1 | 1 |
| Protocol violation | 0 | 1 | 1 |
| Consent withdrawal (not due to an adverse event) | 9 | 3 | 12 |
| Migrated/moved from study area | 6 | 2 | 8 |
| Lost to follow-up (subjects with incomplete vaccination course) | 0 | 0 | 0 |
| Lost to follow-up (subjects with complete vaccination course) | 0 | 3 | 3 |
| Other - not reached | | | |
| Other - practical difficulty this year | | | |

Vaccinated = number of subjects who were vaccinated in the study

Completed = number of subjects who completed Visit 4

Withdrawn = number of subjects who did not come for Visit 4

Template 3 Number of subjects at each visit and list of withdrawn subjects up to visit 4 – First year conclusion (Total vaccinated cohort)

| Group | VISIT | N | Withdrawn Subject numbers | Reason for withdrawal |
|---------|---------|-----|------------------------------|----------------------------|
| HRV | VISIT 1 | 508 | | |
| | | | no. PP | CONSENT WITHDRAWAL |
| | | | no. PP | CONSENT WITHDRAWAL |
| | | | no. PPD | CONSENT WITHDRAWAL |
| | VISIT 2 | 504 | no. PPD | CONSENT WITHDRAWAL |
| | | | no. PPD | CONSENT WITHDRAWAL |
| | | | no. PPD | SERIOUS ADVERSE EXPERIENCE |
| | VISIT 3 | 501 | | |
| | | | no. PP | MIGRATION FROM STUDY AREA |
| | | | no. PP | CONSENT WITHDRAWAL |
| | | | no. PP | MIGRATION FROM STUDY AREA |
| | | | no. PP | CONSENT WITHDRAWAL |
| | | | no. PP | MIGRATION FROM STUDY AREA |
| | | | no. PPD | CONSENT WITHDRAWAL |
| | | | no. PPD | MIGRATION FROM STUDY AREA |
| | | | no. PPD | MIGRATION FROM STUDY AREA |
| | | | | |
| Placebo | VISIT 4 | 492 | | |
| | | | | |
| | VISIT 1 | 257 | | |
| | | | no. PP | PROTOCOL VIOLATION |
| | VISIT 2 | 255 | no. PPD | CONSENT WITHDRAWAL |
| | | | | |
| | | | no. PPD | CONSENT WITHDRAWAL |
| | | | | |
| | VISIT 3 | 254 | | |
| | | | no. PP | MIGRATION FROM STUDY AREA |
| | | | no. PP | LOST TO FOLLOW-UP |
| | | | no. PP | LOST TO FOLLOW-UP |
| | | | no. PP | CONSENT WITHDRAWAL |
| | | | no. PP | MIGRATION FROM STUDY AREA |
| | | | no. PPD | LOST TO FOLLOW-UP |
| | | | no. PPD | ADVERSE EXPERIENCE |
| | VISIT 4 | 247 | | |

Template 4 Number of subjects in the sub-cohorts (Total vaccinated cohort)

| | | HRV N = 1666 | | Placebo N = 1667 | | Total N = 3333 | |
|-----------------|-----------------------------|-----------------|------|---------------------|------|-------------------|------|
| Characteristics | Categories | n | % | n | % | n | % |
| Sub-cohort | Immunogenicity sub cohort 1 | 306 | 18.4 | 306 | 18.4 | 612 | 18.4 |
| | Immunogenicity sub cohort 2 | 153 | 9.2 | 153 | 9.2 | 306 | 9.2 |

N = number of subject number

n = number of subject number in a given category

% = $n / \text{Number of subject number with available results} \times 100$

Template 5 Number of subjects enrolled into the study as well as the number excluded from ATP analyses (Reactogenicity/Safety and Immunogenicity) with reasons for exclusion

| Title | Total | | | HRV | | Placebo | |
|--|-------|-----|-----|-----|-----|---------|-----|
| | n | s | % | n | s | n | s |
| Total cohort | 765 | | | | | | |
| Total vaccinated cohort | 765 | | 100 | 508 | | 257 | |
| Randomisation code broken at the investigator site (code 1060) | 1 | 1 | | 1 | 1 | 0 | 0 |
| Essential serological data missing (code 2100) | 3 | 3 | | 3 | 3 | 0 | 0 |
| Subject not planned to be bled for their all blood sampling visits (code 2130) | 707 | 708 | | 470 | 471 | 237 | 237 |
| ATP cohort for immunogenicity | 54 | | 7.1 | 34 | | 20 | |

Note: Subjects may have more than one elimination code assigned

n = number of subjects with the elimination code assigned excluding subjects who have been assigned a lower elimination code number

s = number of subjects with the elimination code assigned

% = percentage of subjects in the considered ATP cohort relative to the Total vaccinated cohort

Template 6 Summary of demographic characteristics (ATP cohort for Immunogenicity)

| | | HRV N = 34 | | Placebo N = 20 | | Total N = 54 | |
|----------------------------------|---|---------------|------|-------------------|------|-----------------|------|
| Characteristics | Parameters or Categories | Value or n | % | Value or n | % | Value or n | % |
| Age (weeks) at Dose 1 of HRV | Mean | 7.5 | - | 7.2 | - | 7.4 | - |
| | SD | 1.60 | - | 1.23 | - | 1.47 | - |
| | Median | 7.0 | - | 7.0 | - | 7.0 | - |
| | Minimum | 6 | - | 6 | - | 6 | - |
| | Maximum | 12 | - | 10 | - | 12 | - |
| Age (weeks) at Dose 2 of HRV | Mean | 12.7 | - | 12.0 | - | 12.4 | - |
| | SD | 1.57 | - | 1.45 | - | 1.55 | - |
| | Median | 12.0 | - | 12.0 | - | 12.0 | - |
| | Minimum | 11 | - | 10 | - | 10 | - |
| | Maximum | 11 | - | 10 | - | 10 | - |
| | Missing | 17 | - | 15 | - | 17 | - |
| Age (weeks) at Dose 1 of DPT-IPV | Mean | 12.7 | - | 12.0 | - | 12.4 | - |
| | SD | 1.57 | - | 1.45 | - | 1.55 | - |
| | Median | 12.0 | - | 12.0 | - | 12.0 | - |
| | Minimum | 11 | - | 10 | - | 10 | - |
| | Maximum | 11 | - | 10 | - | 10 | - |
| | Missing | 17 | - | 15 | - | 17 | - |
| Age (weeks) at Dose 2 of DPT-IPV | Mean | | | | | | |
| | SD | | | | | | |
| | Median | | | | | | |
| | Minimum | | | | | | |
| | Maximum | | | | | | |
| | Missing | | | | | | |
| Age (weeks) at Dose 3 of DPT-IPV | Mean | | | | | | |
| | SD | | | | | | |
| | Median | | | | | | |
| | Minimum | | | | | | |
| | Maximum | | | | | | |
| | Missing | | | | | | |
| Gender | Female | 14 | 41.2 | 14 | 70.0 | 28 | 51.9 |
| | Male | 20 | 58.8 | 6 | 30.0 | 26 | 48.1 |
| Geographical ancestry | African heritage / African American | 0 | - | 0 | - | 0 | - |
| | American Indian or Alaskan native | 0 | - | 0 | - | 0 | - |
| | Asian - Central/South Asian heritage | 0 | - | 0 | - | 0 | - |
| | Asian - East Asian heritage | 0 | - | 0 | - | 0 | - |
| | Asian - Japanese heritage | 34 | 100 | 20 | 100 | 54 | 100 |
| | Asian - South east Asian heritage | 0 | - | 0 | - | 0 | - |
| | Native Hawaiian or other Pacific Islander | 0 | - | 0 | - | 0 | - |
| | White - Arabic / North African heritage | 0 | - | 0 | - | 0 | - |
| | White - Caucasian / European heritage | 0 | - | 0 | - | 0 | - |
| | Other | 0 | - | 0 | - | 0 | - |

| | | HRV N = 34 | | Placebo N = 20 | | Total N = 54 | |
|-------------------------------------|--------------------------|---------------|---|-------------------|---|-----------------|---|
| Characteristics | Parameters or Categories | Value or n | % | Value or n | % | Value or n | % |
| Height (cm) at visit 1 | Mean | 55.3 | - | 55.7 | - | 55.5 | - |
| | SD | 3.80 | - | 1.87 | - | 3.21 | - |
| | Median | 55.5 | - | 55.0 | - | 55.0 | - |
| Weight (kg) at visit 1 | Mean | 5.2 | - | 5.1 | - | 5.1 | - |
| | SD | 0.66 | - | 0.49 | - | 0.60 | - |
| | Median | 5.1 | - | 5.2 | - | 5.2 | - |
| BMI at visit 1 (kg/m ²) | Mean | | | | | | |
| | SD | | | | | | |
| | Median | | | | | | |
| Gestational age (weeks) | Mean | | | | | | |
| | SD | | | | | | |
| | Median | | | | | | |
| | Minimum | | | | | | |
| | Maximum | | | | | | |

N = total number of subjects in each group

n = number of subjects in a given category

Value = value of the considered parameter

% = n / Number of subjects with available results x 100

SD= standard deviation

Database Lock Date = 31MAR2009

Template 7 Minimum and maximum activity dates (Total vaccinated cohort)

| Visit | Minimum date | Maximum date |
|-------|--------------|--------------|
| 1 | 19JUN2007 | 29DEC2007 |
| 2 | 24JUL2007 | 08FEB2008 |
| 3 | 24AUG2007 | 18MAR2008 |
| 4 | 25MAR2008 | 22NOV2008 |
| 5 | 24MAR2009 | 31MAR2009* |

*Database Lock Date = 31MAR2009

Template 8 Deviations from specifications for age and intervals between study visits (Total vaccinated cohort)

| | | Age | PRE-Dose:1 | Dose:1-Dose:2 | | Dose:2-PII(M2) | |
|---------|----------|--------------------|------------------|--------------------|--------------------|--------------------|--------------------|
| Group | Protocol | Protocol | Protocol | Adapted | Protocol | Adapted | |
| | | from 6 to 14 weeks | from 0 to 0 days | from 30 to 48 days | from 21 to 48 days | from 30 to 48 days | from 21 to 48 days |
| HRV | N | 508 | 37 | 499 | 499 | 35 | 35 |
| | n | 0 | 0 | 0 | 0 | 0 | 0 |
| | % | 0.0 | 0.0 | 0.0 | 0.0 | 0.0 | 0.0 |
| | range | 6 to 14 | 0 to 0 | 30 to 47 | 30 to 47 | 30 to 45 | 30 to 45 |
| Placebo | N | 257 | 20 | 250 | 250 | 20 | 20 |
| | n | 1 | 0 | 0 | 0 | 0 | 0 |
| | % | 0.4 | 0.0 | 0.0 | 0.0 | 0.0 | 0.0 |
| | range | 5 to 14 | 0 to 0 | 30 to 47 | 30 to 47 | 30 to 42 | 30 to 42 |

Adapted = interval used for defining the ATP cohorts for immunogenicity

N = total number of subjects with available results

n (%) = number / percentage of subjects with results outside of the interval

range = minimum-maximum for age and intervals

PRE = pre-vaccination

PII(M2) = One month after the second dose (Visit 3)

Template 9 Study population (Total vaccinated cohort)

| Number of subjects | [each group] | Total |
|--|--------------|-------|
| Planned, N | | |
| Randomised, N (<Total Vaccinated Cohort>) | | |
| Completed, n (%) | | |
| Demographics | | |
| N (<Total Vaccinated Cohort>) | | |
| Females:Males | | |
| Mean Age, <years> (SD) | | |
| Median Age, <years> (minimum, maximum) | | |
| <Most frequent category of race>, n (%) | | |
| <Second most frequent category of race>, n (%) | | |
| <Third most frequent category of race>, n (%) | | |

[each group]:

Short group label= long group label

Template 10 Anti-rotavirus IgA antibody GMC and seropositivity rates - ATP cohort for immunogenicity

| | | | $\geq 20 \text{ U/mL}$ | | | | GMC | | | |
|---------|---------|----|------------------------|------|--------|------|-------|-------|--------|--|
| | | | | | 95% CI | | | | 95% CI | |
| Group | Timing | N | n | % | LL | UL | value | LL | UL | |
| HRV | PRE | 34 | 0 | 0.0 | 0.0 | 10.3 | <20 | - | - | |
| | PII(M2) | 34 | 29 | 85.3 | 68.9 | 95.0 | 217.0 | 109.9 | 428.6 | |
| Placebo | PRE | 20 | 0 | 0.0 | 0.0 | 16.8 | <20 | - | - | |
| | PII(M2) | 20 | 1 | 5.0 | 0.1 | 24.9 | <20 | - | - | |

GMC = geometric mean antibody concentration calculated on all subjects

N = number of subjects with available results

n (%) = number (percentage) of subjects with concentration $\geq 20 \text{ U/mL}$

95% CI = 95% confidence interval; LL = Lower Limit, UL = Upper Limit

PII (M2) = One month after the second dose (Visit 3)

PRE = pre-vaccination

Template 11 Anti-rotavirus IgA antibody GMC calculated on subjects seropositive for anti-rotavirus IgA antibodies - ATP cohort for immunogenicity

| | | | | | | GMC | | | 95% CI | | |
|---------|---------|----|-------|--|--|-------|--|--|--------|--|--|
| Group | Timing | N | value | | | LL | | | UL | | |
| HRV | PII(M2) | 29 | 368.9 | | | 202.1 | | | 673.3 | | |
| Placebo | PII(M2) | 1 | 496.0 | | | - | | | - | | |

GMC = geometric mean antibody concentration calculated on subjects with concentration $\geq 20 \text{ U/mL}$

N = number of subjects who seroconverted for Anti-rotavirus IgA Antibody

95% CI = 95% confidence interval; LL = Lower Limit, UL = Upper Limit

PII (M2) = One month after the second dose (Visit 3)

Template 12 Seroprotection rates and GMC for anti-Diphtheria and anti-Tetanus antibody concentrations by groups at pre booster vaccination (ATP cohort for analysis of antibody persistence)

| | | | $\geq 0.1 \text{ IU/ml}$ | | | | $\geq 1 \text{ IU/ml}$ | | | | GMC | | | |
|------------------|---------|---------|--------------------------|-----|--------|------|------------------------|----|--------|-----|-----|-------|--------|-------|
| | | | | | 95% CI | | | | 95% CI | | | | 95% CI | |
| Antibody | Group | Timing | N | n | % | LL | UL | n | % | LL | UL | value | LL | UL |
| Anti- Diphtheria | Group A | Pre-BST | 271 | 241 | 88.9 | 84.6 | 92.4 | 1 | 0.4 | 0.0 | 2.0 | 0.175 | 0.163 | 0.188 |
| | Group B | Pre-BST | 272 | 250 | 91.9 | 88.0 | 94.9 | 0 | 0.0 | 0.0 | 1.3 | 0.189 | 0.176 | 0.202 |
| | Control | Pre-BST | 279 | 234 | 83.9 | 79.0 | 88.0 | 2 | 0.7 | 0.1 | 2.6 | 0.154 | 0.142 | 0.166 |
| Anti-Tetanus | Group A | Pre-BST | 272 | 269 | 98.9 | 96.8 | 99.8 | 8 | 2.9 | 1.3 | 5.7 | 0.450 | 0.423 | 0.478 |
| | Group B | Pre-BST | 273 | 271 | 99.3 | 97.4 | 99.9 | 10 | 3.7 | 1.8 | 6.6 | 0.509 | 0.481 | 0.540 |
| | Control | Pre-BST | 278 | 275 | 98.9 | 96.9 | 99.8 | 6 | 2.2 | 0.8 | 4.6 | 0.380 | 0.359 | 0.404 |

Group A = Subjects who received DTPa-IPV/Hib vaccine at 2, 3, 4 months of age in the primary study

Group B = Subjects who received DTPa-IPV/Hib vaccine at 3, 4, 5 months of age in the primary study

Control = Subjects who received DTPa/Hib + IPV vaccines at 2, 3, 4 months of age in the primary study

Seroprotection=Anti-Diphtheria and Anti-Tetanus antibody concentration $\geq 0.1 \text{ IU/ml}$

GMC = geometric mean antibody concentration calculated on all subjects

N = number of subjects with available results

n/% = number/percentage of subjects with concentration equal to or above specified value

95% CI = 95% confidence interval; LL = Lower Limit, UL = Upper Limit

Pre-BST=Pre-booster vaccination blood sampling time point

Template 13 Seropositivity rates and GMC for anti-PT by groups at pre booster vaccination (ATP cohort for analysis of antibody persistence)

| | | | | ≥ 2.693 IU/mL | | | | ≥ 10 IU/mL | | | | GMC | | | |
|----------|---------|---------|-----|--------------------|------|------|------|-----------------|------|------|------|--------|------|------|--|
| | | | | 95% CI | | | | 95% CI | | | | 95% CI | | | |
| Antibody | Group | Timing | N | n | % | LL | UL | n | % | LL | UL | value | LL | UL | |
| Anti-PT | Group A | Pre-BST | 272 | 260 | 95.6 | 92.4 | 97.7 | 38 | 14.0 | 10.1 | 18.7 | 10.3 | 9.6 | 11.1 | |
| | Group B | Pre-BST | 273 | 263 | 96.3 | 93.4 | 98.2 | 62 | 22.7 | 17.9 | 28.1 | 12.2 | 11.3 | 13.1 | |
| | Control | Pre-BST | 280 | 260 | 92.9 | 89.2 | 95.6 | 43 | 15.4 | 11.3 | 20.1 | 10.4 | 9.6 | 11.2 | |

Group A = Subjects who received DTPa-IPV/Hib vaccine at 2, 3, 4 months of age in the primary study

Group B = Subjects who received DTPa-IPV/Hib vaccine at 3, 4, 5 months of age in the primary study

Control = Subjects who received DTPa/Hib + IPV vaccines at 2, 3, 4 months of age in the primary study

Seropositivity =Anti-PT antibody concentration ≥ 5 ELU/ml

GMC = geometric mean antibody concentration calculated on all subjects

N = number of subjects with available results

n/% = number/percentage of subjects with concentration equal to or above specified value

95% CI = 95% confidence interval; LL = Lower Limit, UL = Upper Limit

Pre-BST=Pre-booster vaccination blood sampling time point

Template 14 Seroprotection rates and geometric mean titres (GMT) for anti-Polioivirus 1, 2 and 3 antibody by groups at pre vaccination (ATP cohort for analysis of antibody persistence)

| | | | | ≥ 8 ED ₅₀ | | | | GMT | | | |
|--------------------|---------|---------|-----|---------------------------|------|------|------|--------|------|-------|--|
| | | | | 95% CI | | | | 95% CI | | | |
| Antibody | Group | Timing | N | n | % | LL | UL | value | LL | UL | |
